7.0 Toxicity Management & Dose Modifications

At each visit during the Treatment Period, subjects should first be evaluated for the occurrence of AEs and laboratory abnormalities. The potential causes of the adverse events should be thoroughly investigated and confounding factors should be identified and eliminated whenever possible.

Treatment emergent hypertension or proteinuria is relatively common in subjects receiving pazopanib and is handled by dose modification of pazopanib. Some adverse events, although rare, can result in significant clinical consequence such as arterial/venial thrombosis, severe hemorrhage, bowel perforation and severe fatigue/asthenia, therefore should be promptly identified and managed. Some clinical signs and symptoms may be early indicators for severe toxicity that should be thoroughly investigated (e.g., abdominal pain may be an early sign for bowel perforation).

Specific recommendations for management of these possible AEs along with guidelines for dose delay/modification or discontinuation of study treatment are provided in Tables 2 and 3.

If dose reduction of pazopanib is necessary, the dose should be reduced stepwise by 200 mg at each step, and the subject should be monitored for 10 to 14 days at each dose level. If toxicity does not abate during this monitoring time, pazopanib may need to be interrupted and/or the dose further decreased with continued monitoring for an additional 10-14 days at each dose level, and so on.

If the toxicity has abated with reduction of the dose and dose re-escalation is considered safe by the investigator, the dose can then be increased step-wise back to the pre-event dose (in 200 mg increments, after monitoring for 10-14 days at each dose level to ensure that toxicity did not recur or worsen).

If a subject's treatment has been interrupted for more than 21 days, the Investigator must contact the PI to review the subject's condition in order to resume the treatment.

Dose Interruptions/Modifications for Specific, Non-liver Related, Toxicities

Recommendations for investigational product dose interruptions/modifications in case of specific treatment-emergent AEs are provided in Table 2.

Table 2 Dose Modification Algorithms for Potential Treatment-Related Adverse Events

AE Terms & Descriptions	Dose Modification Algorithms
Hypertension^a	

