(A). Asymptomatic and persistent SBP of ≥ 150 and < 170 mmHg, or DBP ≥ 90 and < 110 mmHg.	Step 1. Continue investigational product pazopanib at the current dose. Step 2. Adjust current or initiate new antihypertensive medication(s). Step 3. Titrate antihypertensive medication(s) during next 2 weeks as indicated to achieve well-controlled ^b blood pressure (BP). If BP is not well-controlled within 2 weeks, consider referral to a specialist and go to scenario (B).
(B). Asymptomatic SBP ≥ 170 mmHg, or DBP ≥ 110 mmHg, or failure to achieve well-controlled BP within 2 weeks in scenario (A).	Step 1. Interrupt pazopanib.. Step 2. Adjust current or initiate new antihypertensive medication(s). Step 3. Titrate antihypertensive medication(s) during next 2 weeks as indicated to achieve well-controlled BP. Step 4. Once BP is well-controlled, restart pazopanib dose-reduced by 200 mg.
(C). Symptomatic hypertension or recurring SBP ≥ 170 mmHg, or DBP ≥ 110 mmHg, despite modification of antihypertensive medication(s)	Step 1. Interrupt pazopanib Step 2. Adjust current or initiate new antihypertensive medication(s). Step 3. Titrate antihypertensive medication(s) during next 2 weeks as indicated to achieve well-controlled BP. Referral to a specialist for further evaluation and follow-up is also recommended. Step 4. Once BP is well-controlled, restart pazopanib dose-reduced by 200 mg.
(D). Refractory hypertension unresponsive to above interventions.	Discontinue pazopanib and continue follow-up per protocol.
Proteinuria	
UPC ≥ 3 grams or 24-hr urine protein ≥ 3 grams	Step 1. Interrupt pazopanib. Step 2. Test weekly the 24-hour urine protein until the level is < 3 grams. Then, restart pazopanib, dose reduced by 200 mg. Step 3. If 24-hour urine protein ≥ 3 grams recurs, repeat Steps 1 and 2. Step 4. If 24-hour urine protein ≥ 3 grams recurs and the pazopanib dose can no longer be reduced, discontinue pazopanib and continue follow up per protocol.

Hemorrhage /Bleeding

Grade 1

For hemoptysis, interrupt pazopanib and contact the study PI to discuss whether further treatment with pazopanib is appropriate.

Continue pazopanib with current dose; monitor as clinically indicated.

Grade 2

Step 1. If pulmonary or GI bleed (other than hemorrhoidal bleeding), discontinue pazopanib and continue follow-up per protocol. Otherwise, interrupt pazopanib until the AE resolved to \leq Grade 1.

Step 2. Restart pazopanib; consider reducing dose and monitor as clinically indicated.

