Grade 3 or 4, or Recurrent \geq Grade 2 event after dose interruption/reduction.

Discontinue pazopanib and continue with follow-up per protocol.

Venous Thrombosis (DVT, PE)

Grade 1 and 2

Continue pazopanib with same dose; initiate and monitor anticoagulation as clinically indicated.

Grade 3 or >

Discontinue pazopanib and continue follow-up per protocol.

Grade 4 and/or PE

Discontinue pazopanib and continue follow-up per protocol.

Arterial Thrombosis/Ischemia

Any Grade

Discontinue pazopanib and continue follow-up per protocol.

Thrombocytopenia: Investigate and document underlying cause

Grade 1 or 2

Continue pazopanib with current dose; monitor as clinically indicated.

Grade 3 or 4

Step 1. Interrupt pazopanib until toxicity resolves to \leq Grade 2.
Step 2. Restart pazopanib dose-reduced by 200 mg and monitor as clinically indicated.

If no recovery to \leq Grade 2 or recurrent Grade 3 or 4 thrombocytopenia, discontinue pazopanib and follow-up per protocol

Anemia: No specific dose reduction rules are indicated for anemia unless due to hemorrhage or bleeding as noted above.

Palmar-plantar Erythrodysesthesia Syndrome

Grade 1	1. Continue IP at present dose
Minimal skin changes or dermatitis without pain (erythema, oedema, hyperkeratosis)	
Grade 2	1. Hold IP 2. Treat as clinically appropriate 3. Upon resolution to Level 1 or better restart IP with a dose reduction to 400 mg 4. If recurrent consider a further dose reduction to 200mg or discontinuation
Skin changes with pain; limiting instrumental activities of daily living (ADLs) (peeling, blisters, oedema, bleed, hyperkeratosis)	
Grade 3	1. Discontinue IP
Severe skin changes with pain and limiting self care	

Other Clinically Significant Adverse Events ^c

Grade 1	Continue pazopanib; monitor as clinically indicated.
Grade 2 or 3, if clinically significant	Step 1. Interrupt pazopanib until toxicity resolves to \leq Grade 1. Step 2. Restart pazopanib dose-reduced by 200 mg and monitor as clinically indicated.
Grade 4	Discontinue pazopanib and continue follow-up per protocol.

Prolongation of QTc Interval: If the QTc is prolonged, the ECG should be manually read to ensure accuracy of the reading. The values below refer to manually-read ECGs.

QTc \geq 480 < 500 msec	Continue pazopanib; monitor as clinically indicated.
QTc \geq 500 msec	Discontinue pazopanib and continue follow-up per protocol.
a.	Patients are encouraged to self-monitor BP twice a week

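### Table 2 has no bowel perforation row although Section 7.0 points to one, so a Grade 2-3 perforation that resolves defaults to restart at a dose 200 mg lower

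*Combined protocol and SAP*

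**What the plan says.** Section 7.0 lists rare events with serious clinical consequences: thrombosis, "severe hemorrhage, bowel perforation and severe fatigue/asthenia, therefore should be promptly identified and managed". It adds that abdominal pain may be an early sign of perforation. It then says of the events it has discussed, with reference to Tables 2 and 3: "Specific recommendations for management of these possible AEs along with guidelines for dose delay/modification or discontinuation of study treatment are provided".

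Table 2 has rows for hypertension, proteinuria, hemorrhage, venous thrombosis, arterial thrombosis/ischemia, thrombocytopenia, anemia, palmar-plantar erythrodysesthesia, other clinically significant adverse events, and QTc. Table 3 covers liver events only. Appendix III covers diarrhea, nausea and vomiting.

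The row for other adverse events has a tier labelled "Grade 2 or 3, if clinically significant". Step 1 is to interrupt until the toxicity is Grade 1 or less. Step 2 is: "Restart pazopanib dose-reduced by 200 mg and monitor as clinically indicated". Grade 4 means discontinuation. The general text of Section 7.0 adds: "If a subject's treatment has been interrupted for more than 21 days, the Investigator must contact the PI" before treatment resumes.

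For a Grade 2 hemorrhage, Table 2 says: "If pulmonary or GI bleed (other than hemorrhoidal bleeding), discontinue pazopanib and continue follow-up per protocol".

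**The concern.** The text refers the investigator to a specific rule that is not there. Thrombosis and hemorrhage, named in the same sentence as perforation, each have their own rows, and those rows stop the drug for the more serious forms. Perforation is left to a catch-all whose written default after recovery is to give the drug again.

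What is at stake is patient safety and consistent handling at the two sites. Section 1.2 lists bowel perforation among the causes of death from serious adverse events that were more common on pazopanib than on placebo in the randomized renal cell trial. No sample size, error rate or estimate depends on this point.

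**Working it through.** There is no figure in the plan to reproduce. The check is a reading of every row of Tables 2 and 3, Appendix III and every mention of perforation, followed by a comparison grade by grade.

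**Step 1: is there a perforation rule anywhere?** Perforation appears in Section 1.2 (safety background), Section 3.3 (exclusions 5d and 5e) and the introduction to Section 7.0. None of these says what to do with pazopanib after an on-study perforation.

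**Step 2: which rule applies by default?**
- Perforation with a Grade 2 or higher GI bleed: the hemorrhage rows apply, so discontinue.
- Grade 4: the row for other events applies, so discontinue.
- Clinically significant Grade 2 or 3 without such a bleed: the row for other events applies, so interrupt until Grade 1 or less, then restart 200 mg lower.

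The gap is the third case only.

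**Step 3: compare with the named events that have a CTCAE-graded rule in Table 2.** Hypertension, proteinuria and QTc are left out because the table does not manage them by CTCAE grade. Anemia is left out because it has no rule of its own.

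| Event | Grade 2 | Grade 3 |
|---|---|---|
| Hemorrhage | Discontinue if pulmonary or non-hemorrhoidal GI; otherwise interrupt and restart | Discontinue |
| Venous thrombosis | Continue at same dose (discontinue if pulmonary embolism) | Discontinue |
| Arterial thrombosis/ischemia | Discontinue | Discontinue |
| Palmar-plantar erythrodysesthesia | Hold, restart at 400 mg | Discontinue |
| Thrombocytopenia | Continue | Interrupt, restart 200 mg lower |
| **Perforation (default row)** | **Interrupt, restart 200 mg lower** | **Interrupt, restart 200 mg lower** |

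At Grade 3, 4 of 5 named events stop the drug; only thrombocytopenia allows a restart. At Grade 2, 1 of 5 always stops the drug (arterial thrombosis). Part of a second does so (pulmonary or GI bleeding), as does venous thrombosis when it is a pulmonary embolism.

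**Step 4: is there a minimum wait or a required approval?** The default row makes restart conditional on recovery and sets no number of days. The 21-day rule requires contact with the PI after a long interruption; it is not a minimum wait. The 10 to 14 days of monitoring in Section 7.0 follow a dose reduction and do not delay a restart. By contrast, even Grade 1 hemoptysis calls for interruption and a discussion with the study PI.

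**The case against.** The best defense is that the catch-all row is how the protocol is built. Severe fatigue/asthenia, named in the same sentence, has no row either, so a named event without its own row is not unique to perforation. What is missing is a specific rule, not any rule. This stands, but interrupt-and-reduce suits fatigue far better than it suits perforation, and the text promises specific recommendations.

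Second, the tables are recommendations and guidelines. They do not oblige an investigator to re-dose, and most would stop. Section 5.2 ends treatment for unresolved toxicity, and Section 8.4 foresees removal for unacceptable adverse events. This also stands. It limits the hazard but does not supply the rule for a perforation that has resolved.

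Third, oversight is real. Sites report SAEs to the Sponsor-Investigator within one business day (Section 16.2.2). Suspected serious reactions go to ongoing DSMC review, and significant toxicities and dose adjustments are discussed monthly (Section 16.2.1). None of these says whether or when to restart.

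Three stronger readings are tempting, and the documents do not support them:
- *Restart is unconditional.* It is not; recovery to Grade 1 or less comes first. Nor is the lack of a fixed wait peculiar to perforation, since Table 2's restart rules generally depend on recovery.
- *The default is laxer than Table 2 as a whole.* That holds at Grade 3. At Grade 2 it holds against the two closest comparators only.
- *It contradicts exclusion 5e, which bars a perforation within 28 days before starting treatment.* Entry criteria do not govern re-dosing. At most, a restart could fall inside an interval that the protocol treats as too early for a first dose.

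**Conclusion.** The point holds in a narrow form. The perforation row that Section 7.0 leads the reader to expect is missing, and the default for a clinically significant Grade 2-3 event without a Grade 2 or higher GI bleed is restart after recovery. At Grade 3 that is out of line with 4 of 5 comparable events, including a skin reaction. At Grade 2 it is out of line with non-hemorrhoidal GI bleeding and arterial thrombosis only.

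Confidence is high for the missing row. It is moderate for the re-dosing hazard, which assumes that a perforation is graded 2 or 3 under CTCAE v4.0 and later counts as Grade 1 or less. Section 9.2 and Appendix II refer to that scale without reproducing its perforation grades.

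The event is rare. Section 1.2 puts it at 1% or less in a monotherapy profile based on 225 renal cell cancer subjects. If that rate carried over to 30 breast cancer patients on the combination, which is an assumption the documents do not test, the expected number would be at most 30 × 0.01 = 0.3 perforations of any grade, and fewer in the gap described here. The primary endpoint is essentially unaffected. This is a low-cost patient-safety correction that should be made.

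**What to change.** Add one row to Table 2: *Gastrointestinal perforation, any grade*, with the same action as the arterial thrombosis row (stop pazopanib permanently and keep the patient in protocol follow-up). This matches how the table already treats a Grade 2 GI bleed, removes the dependence on how a perforation is graded, and makes the reference in Section 7.0 true for this event.

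The cost is a one-row protocol amendment, with no added visits, tests or patients. The downside is that a patient who recovers from a perforation cannot be re-treated with pazopanib on study.

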5.0 Investigational Treatment Plan

5.1 Dose and Schedule

Pazopanib, 800 mg a day by mouth

Letrozole 2.5 mg, **OR** anastrozole 1 mg a day by mouth;

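### The hand-foot row of Table 2 does not follow the 200 mg step in Section 7.0 and cannot be applied below 600 mg; the venous thrombosis rows also overlap for low-grade pulmonary embolism

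*Combined protocol and SAP*

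**What the plan says.** **General rule.** Section 5.1 sets the starting dose: "Pazopanib, 800 mg a day by mouth". Section 7.0 then says that, if a reduction is needed, "the dose should be reduced stepwise by 200 mg at each step", with 10 to 14 days of monitoring at each level. Re-escalation is also in 200 mg increments, with its own conditions. Section 7.0 describes Tables 2 and 3 as giving specific recommendations for particular events. It does not say that they override the general step.

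**Hand-foot syndrome (Table 2, Palmar-plantar Erythrodysesthesia Syndrome).** For Grade 2 the drug is held, and then: "Upon resolution to Level 1 or better restart IP with a dose reduction to 400 mg". The next line reads: "If recurrent consider a further dose reduction to 200mg or discontinuation".

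**Other rows of Table 2.** Where the rows for hypertension, proteinuria, thrombocytopenia and other clinically significant events state the size of a reduction, it is by 200 mg.

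**Venous thrombosis (Table 2).** The block heading names both DVT and PE. For Grades 1 and 2 the instruction is: "Continue pazopanib with same dose; initiate and monitor anticoagulation as clinically indicated". The Grade 3 or higher row says to discontinue. The last row, labelled "Grade 4 and/or PE", also says to discontinue.

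**The concern.** Most of Table 2 gives a reduction as a decrement, whereas the hand-foot row gives it as a destination. A decrement can be applied at any dose above the lowest permitted level. A fixed destination produces a different change at each current dose, and it is a reduction only for someone above it. Two investigators could each follow the text faithfully and restart the same patient at different doses, and a monitor could not say which of them had deviated.

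The venous thrombosis block has a different fault. Two of its rows carry different actions, and their conditions are not mutually exclusive as written.

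What is at stake is whether a stated dosing rule can be carried out, and carried out the same way at UCSF and Yale.

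**Working it through.** The plan gives no numerical figure to reproduce here. The check is dose arithmetic and a reading of the table rows.

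**Step 1. Hand-foot syndrome, Grade 2, first restart.** Let D be the current daily dose. The inputs are the 800 mg start (Section 5.1), the 200 mg step (Section 7.0) and the 400 mg target (Table 2). The general rule gives D − 200. The hand-foot row gives 400, a change of 400 − D.

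| Current dose D | Section 7.0: D − 200 | Hand-foot row | Change under the row |
|---|---|---|---|
| 800 mg | 600 mg | 400 mg | −400 mg (two steps) |
| 600 mg | 400 mg | 400 mg | −200 mg (one step) |
| 400 mg | 200 mg | 400 mg | 0 (no reduction) |
| 200 mg | 0 mg by arithmetic | 400 mg | +200 mg (not a reduction) |

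The two texts agree only at 600 mg. At 800 mg, where every patient starts, they differ by 200 mg, and the row passes over the 600 mg level with its monitoring period. Section 7.0 names no lowest dose, so the general rule has no stated end point at 200 mg either.

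**Step 2. Can a patient be at 400 or 200 mg before the first hand-foot event?** Yes. Two reductions by 200 mg for other toxicities give 800 − 2 × 200 = 400 mg, and three give 800 − 3 × 200 = 200 mg. Section 7.0 allows repeated steps, and the proteinuria row plans for a dose that cannot be lowered further. The 200 mg line in the hand-foot row is for recurrence, so it does not cover a first event in such a patient.

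**Step 3. Venous thrombosis rows side by side.**

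| Row condition | Excludes PE? | Grade limit for PE? | Action |
|---|---|---|---|
| Grade 1 and 2 | No | Grades 1 and 2 | Continue, same dose |
| Grade 3 or higher | No | Grade 3 and above | Discontinue |
| Grade 4 and/or PE | No (names PE) | None | Discontinue |

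A PE graded 1 or 2 satisfies the first and third rows, which give different actions. Grade 4 is covered by both the second and third rows, but the action is the same, so that overlap does no harm.

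**Step 4. Does the PE overlap contain any real events?** Sections 7.0 and 9.2 grade toxicity by CTCAE v4.0. Appendix II cites that scale without reproducing its thromboembolism grades. The documents therefore do not show whether a PE can be recorded as Grade 1 or 2.

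**Step 5. How many patients?** Section 1.2 lists pulmonary embolism among events at 1% or less, in a profile based on renal cell cancer monotherapy. If that rate carried over to this trial (an assumption), the expected number among 27 patients would be at most 27 × 0.01 = 0.27, over all grades. The documents give no rate for hand-foot syndrome.

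**The case against.** The strongest defence is that the hand-foot row is a deliberate exception. Section 7.0 calls the tables specific recommendations, and a specific instruction is normally read ahead of a general one. The row also makes sense as a sequence from the starting dose: 800 mg, then 400 mg, then 200 mg or stop. Section 11.1.4 uses a fixed 400 mg target elsewhere, for strong CYP3A4 inhibitors. A different step for one toxicity is not in itself an error. Much of this stands, and it may well be what was meant. But no sentence states the precedence. Even if it is granted, the row still gives no workable instruction at 400 or 200 mg.

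Likewise, the last venous thrombosis row names PE specifically, so it can be read as governing every PE and leaving the graded rows to other venous events. That is a natural reading, but the heading and the unqualified Grade 1 and 2 row do not say so.

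Three stronger readings are tempting, and the documents do not support them:

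- **That the row orders a dose increase at 200 mg.** It speaks of a reduction, and going from 200 to 400 mg is not one. The row simply leaves such patients uncovered.
- **That the hand-foot texts demand opposite actions.** At the starting dose both lower the dose and differ only in how far. Only the PE rows pair continuing with discontinuing, and only if a low-grade PE can be recorded.
- **That the trial result is at risk.** One patient is 1/27 = 3.7% of the evaluable sample, and success needs 4 responders. But nothing shows that this ambiguity would change a patient's 12-week status. Patients become evaluable after two weeks on treatment (Section 12.2), and stopping pazopanib is not a progression criterion in Section 9.1. Nor is a formal dose-modification analysis planned: Section 12.1 lists safety as adverse events and SAEs, and Section 16.2.1 mentions dose adjustments only as a topic for site committee discussion.

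**Conclusion.** The point holds as an internal inconsistency that should be corrected.

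The hand-foot part is firm. It needs only the starting dose, the 200 mg step and the 400 mg target. The two texts differ by 200 mg at the starting dose and agree at one of four dose levels. At the two lowest levels the row cannot be carried out as written.

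The pulmonary embolism part is secondary. The overlap in wording is literal, but its practical reach is unknown because it depends on CTCAE v4.0 grades that the documents do not give.

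The consequence is for patient safety and consistent conduct across the two sites. Few patients are likely to be affected, though the number with hand-foot syndrome cannot be estimated from the documents. No effect on the primary analysis is shown. The sample size and error rates of the two-stage design do not depend on the dose-modification rules.

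**What to change.** 1. Reconcile the stepwise rule in Section 7.0 with the Grade 2 hand-foot row of Table 2. State which governs, and state what applies to a patient already at or below 400 mg when the event first occurs.
2. Reconcile the venous thrombosis rows so that each event, including each pulmonary embolism, leads to a single action, and remove the duplicate coverage of Grade 4.

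Which dose and which action apply is a clinical decision for the sponsor, and no view is taken on it here. The cost is a wording change to one section and its table, made through a protocol amendment and notified to both sites. It changes neither the sample size nor the planned analyses.
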